3.2 Coding Systems and Conventions

3.2.1 Definition of Baseline

In general, all values recorded at Visit T1 (Day 1) prior to the first dose will be regarded as baseline values for this study. In case no predose Visit T1 (Day 1) value was recorded (expected for ECG and for coagulation parameters), the most recent value prior to Visit T1 (Day 1) will be used as baseline value instead.

For serum or plasma 17-OHP, P, cortisol, A4, ACTH, total T, and 11-ketoT, baseline is defined as the mean of the predose value from Visit T1 (Day 1) and the most recent “0-hour” value prior to Visit T1 (Day 1), if the glucocorticoid dose was the same as at Visit T1 (Day 1) (if not the same, then only the predose Visit T1 (Day 1) value will be used).

For on-site salivary 17-OHP, P, and cortisol, baseline is defined as the mean of the predose value from Visit T1 (Day 1) and the most recent “0-hour” value prior to Visit T1, if the glucocorticoid dose was the same as at Visit T1 (if not the same, then only the predose Visit T1 value will be used). Change from baseline will be calculated for salivary 17-OHP values obtained 30 minutes before, as well as 2 hours and 4 hours after intake of the morning dose of nevanimibe HCl. For additional analyses, baseline for on-site salivary 17-OHP is further categorized by the time of sample relative to the time of the morning dose of nevanimibe HCl. Thus, baseline for the predose measurement on visits T2/T3/T4/T5 is defined for the additional analyses as above, while it is defined as the T1 sample taken 2 hours after the morning dose of nevanimibe HCl for the T2/T3/T4/T5 sample taken 2 hours after the morning dose, and defined as the T1 sample taken 4 hours after the morning dose for the T2/T3/T4/T5 sample taken 4 hours after the morning dose.

For home collection salivary 17-OHP profiles, baseline for the 8 AM (08:00), noon (12:00), 4 PM (16:00), 8 PM (20:00), and 10-11 PM (22:00-23:00) time points is defined as the value obtained for the corresponding time point at Day -8.

Except for the above-mentioned case, all values recorded after the first treatment with the study drug will be regarded as post-baseline values.

3.2.2 Coding of Adverse Events and Medical History

Adverse event (AE) and medical history terms will be assigned a lower level term (LLT) and will be classified by preferred term (PT), high level term (HLT), high level group term (HLGT) and system organ class (SOC) according to the Medical Dictionary for Regulatory Activities (MedDRA) version in effect at the time the database is closed.

3.2.3 Coding of Medications

Frequencies of previous and concomitant medication terms will be given based on Anatomical Therapeutic Chemical Classification (ATC) code levels 1 through 5 according to the Anatomical

Therapeutic Chemical classification system in effect at the time the database is closed. Non-drug treatments will not be coded.

3.2.4 Identification of Prior and Concomitant Medications

Identification of prior and concomitant medications will be done by comparison of the start and stop dates of the medication with the date of first dose of study drug.

- **Prior medications:** If the start date is before date of first dose of study drug, the medication is considered to be a prior medication. If the start date is partially given and unambiguously before start of treatment, the medication is also considered to be a prior medication.
- **Concomitant medications:** If the stop date is the same as or after the date of first dose of study drug or the medication is ongoing, the medication is considered to be a concomitant medication. If the stop date is partially given and not unambiguously before the date of first dose of study drug, the medication is considered to be a concomitant medication. If the stop date is missing and the medication is not known to be ongoing, the medication is considered to be a concomitant medication.

4. Analysis Populations and Subgroups

4.1 Analysis Populations

The statistical analysis is based on the following analysis sets:

All Screened (AS) population: The AS population includes all patients who attended at least one screening visit. The AS population will be used to assess reasons for screening failures and changes in the glucocorticoid dose over time.

Modified Intent-to-Treat (mITT) population: The mITT population includes all subjects who received at least one dose of study drug and had at least one post-baseline serum 17-OHP assessment. The mITT population will be used for all efficacy summarizations.

Per Protocol Population (PPP): The PPP is a subpopulation of the mITT population that includes all subjects who received at least one dose of study drug, had at least one post-baseline serum 17-OHP assessment, were in the treatment period of the study for at least 56 days, were compliant with study drug administration (defined as having taken 80-120% of the assigned study drug dose for at least 8 consecutive weeks (evaluative subjects), and did not have any major protocol deviations that would compromise assessment of efficacy. The PPP will be used to repeat the summarizations of the primary endpoint to assess the impact of compliance with study drug and of major protocol deviations on the obtained data.

Safety Population (SP): The SP includes all subjects who received at least one dose of study drug. The SP will be used for evaluation of all safety parameters.

Pharmacokinetic Population (PKP): The PKP includes all subjects with measurable study drug concentrations.

4.2 Subgroups

Two cohorts (Cohort 1 and Cohort 2) are included in this trial. Eligible subjects are assigned to Cohort 1 if their serum 17-OHP is $\geq 4x$ ULN at the initial screening visit. If this is not the case, subjects may undergo a reduction in glucocorticoid dose and will be reassessed for their serum 17-OHP value. If the serum 17-OHP level is $\geq 4x$ ULN after reassessment, the subject can be enrolled into Cohort 2. No formal group sizes have been appointed for Cohort 1 and 2. All efficacy and PK analyses will be performed overall and by cohort.

Additionally, levels of androstenedione, testosterone and 11-ketotestosterone will be summarized by sex (male, female).

To assess the possible impact of protocol amendment 2 on the safety profile, the analysis of adverse events will be repeated for the subgroup of subjects enrolled according to global amendment 1 and global amendment 2.

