2.1 Study Design

This is a multicenter, intra-subject dose-titration open-label study of nevanimibe hydrochloride (HCl) for the treatment of classic congenital adrenal hyperplasia (CAH). Following a Screening Period, eligible subjects will enter a Baseline and a Treatment Period. During the Treatment Period, subjects will receive nevanimibe HCl twice daily (BID) for 12 or 16 weeks, according to the protocol version (amendment 1 or amendment 2, respectively). Subjects will begin dosing with nevanimibe HCl 1000 mg or 500 mg BID (amendment 1 or amendment 2, respectively). Titration of nevanimibe HCl will depend upon the 17-OHP response, which will be assessed every 4 weeks during the Treatment Period. The dosing regimens are intended to achieve and maintain $17\text{-OHP} \leq 2x$ the upper limit of normal (ULN) (the primary endpoint) on the lowest possible dose of nevanimibe HCl while actively up-titrating if $17\text{-OHP} > 2x$ ULN. Thus, subjects who are found to have met the primary endpoint (i.e., on the previous lower dose of nevanimibe HCl) based on their most recent serum 17-OHP value will have their nevanimibe HCl dose down-titrated to the dose on which they met the endpoint. Four doses of nevanimibe HCl (500 mg BID, 1000 mg BID, 1500 mg BID, and 2000 mg BID) are available for use in the study. The visit and dosing schedules are schematically depicted for amendments 1 and 2 below (Figure 1 and Figure 2).

prednisolone per day. They will then return for Visit S2 to have their 17-OHP level rechecked approximately 2 to 4 weeks after their glucocorticoid dose was changed. If their serum 17-OHP level from Visit S2 is $\geq 4x$ ULN, they will proceed to the Baseline Visit (Visit B1). If not, the case should be discussed with the Medical Monitor.

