6.3 Secondary Efficacy Endpoints

The following are secondary efficacy endpoints:

-Androstenedione, progesterone, total testosterone, and 11-ketotestosterone levels as measured at Baseline, Visit T2 (Day 29), Visit T3 (Day 57), Visit T4 (Day 85), Visit T5 (Day 113; Amendment 2) and Follow-up Visit (Day 113 (Amendment 1) or Day 141 (Amendment 2)); and change from Baseline to Visit T2 (Day 29), Visit T3 (Day 57), Visit T4 (Day 85), Visit T5 (Day 113; Amendment 2) and Follow-up Visit (Day 113 (Amendment 1) or Day 141 (Amendment 2)).

-Serum 17-OHP levels as measured at Visit T1 (Day 1), Visit T2 (Day 29), Visit T3 (Day 57), Visit T4 (Day 85), and Visit T5 (Day 113; Amendment 2) at h0, h1, h2, h3 and h4 (predose and 1-4 hours after administration of the morning replacement glucocorticoid, mineralocorticoid (if applicable), and/or study drug (if applicable) doses); and change from baseline (Visit T1 (Day 1)) to Visit T2 (Day 29), Visit T3 (Day 57), Visit T4 (Day 85), Visit T5 (Day 113; Amendment 2).

-Salivary 17-OHP levels as measured at Visit T1 (Day 1), Visit T2 (Day 29), Visit T3 (Day 57), Visit T4 (Day 85), and Visit T5 (Day 113; Amendment 2) (at time points h0, h2 and h4 (just before, 2 hours after, and 4 hours after (respectively) administration of the morning replacement glucocorticoid (if applicable), mineralocorticoid (if applicable) and/or study drug (if applicable) doses)) and change from Baseline (Visit T1 (Day 1)) to Visit T2 (Day 29), Visit T3 (Day 57), Visit T4 (Day 85), and Visit T5 (Day 113; Amendment 2).

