7.7 Evaluation of Safety Endpoints

All safety variables will be evaluated for the safety population (SP). The analyses of treatment-emergent adverse events (TEAEs) will be performed overall and for subjects enrolled under global

amendment 1 and global amendment 2 separately. The analysis on the SOC and PT level will be repeated for the All Screened population to cover all AEs, also those recorded prior to first treatment with the study drug.

Treatment-emergent adverse events (TEAEs) will be summarized overall and by causal relationship and severity. TEAEs will be coded using the latest MedDRA version at the time of database close. Incidences and percentages will be provided on the subject-level (n), overall as well as on the system organ class (SOC) level and on the preferred term (PT) level for all subjects and by nevanimibe dose category. Results will additionally be prepared by time range. The suitable time ranges will be selected during the DRM for Cohort 1. A subject with more than one AE overall or assigned to one SOC or assigned to one PT will be counted once for the worst category (causal relationship or severity) on the subject level. For the summarization by relationship to study drug, the relationship will be categorized as “related” and “not related,” where related AEs are those with at least a possible relationship to the study treatment. For the summarization by nevanimibe dose, subjects with more than one AE overall or assigned to one SOC or assigned to one PT will be counted once on the subject level at the lowest nevanimibe dose category on which they experience the AE (i.e., a subject with two AEs, one when treated with 1000 mg BID and one when treated with 1500 mg BID, will be counted once at the 1000 mg BID dose). Additionally, the number of AEs per patient-year of treatment will be calculated by nevanimibe dose as (sum of number of AEs of subjects at the respective nevanimibe dose) / (patient-years of treatment at the respective nevanimibe dose).

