7.9 Evaluation of Other Variables

Study drug compliance will be evaluated for the safety population according to the counts of number of tablets dispensed and number of tablets returned, along with the assigned doses of study drug, as recorded in the eCRF. The compliance will be calculated for Visit T1 (Day 1) – Visit T2 (Day 29), Visit T2 (Day 29) – Visit T3 (Day 57), Visit T3 (Day 57) – Visit T4 (Day 85), Visit T4 (Day 85) – Visit T5 (Day 113) and overall (Visit T1 (Day 1) – Visit T4/T5 (Day 85/113)(or early termination date)) as follows:

$$\Delta = (\text{Number of tablets the subject should have taken (based on assigned dose level(s))} - \text{Number of tablets taken})$$

$$\text{Compliance} = \left(1 - \frac{\Delta}{\text{Number of tablets the subject should have taken}}\right) \times 100\%$$

Overall compliance for amendment 1 patients will be calculated from Visit T1 to Visit T4 or early study termination date, while compliance for amendment 2 patients will be calculated from Visit T1 to Visit T5 or early study termination date.

The duration of exposure will be calculated as follows:

$$\text{Duration} = (\text{Date of last dose of study drug} - \text{date of first dose of study drug}) + 1$$

The mean duration of exposure will be calculated overall, by amendment and by cohort.

The duration of treatment in subject-years will be calculated by cohort and by nevanimibe dose as the sum of the duration of exposure of all subjects, overall or in the respective cohort or nevanimibe dose.

All information recorded in the eDiary, including the usage of glucocorticoids and mineralocorticoids, will be listed only.

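### The Amendment 1 versus Amendment 2 adverse-event comparison rests mainly on subject-level percentages over unequal periods, and no all-dose, exposure-adjusted comparison by amendment is specified

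*SAP*

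**What the plan says.** SAP 4.2 gives the amendment split a purpose: "To assess the possible impact of protocol amendment 2 on the safety profile, the analysis of adverse events will be repeated for the subgroup", which is formed separately for each amendment. SAP 7.7 repeats the scope: "The analyses of treatment-emergent adverse events (TEAEs) will be performed overall and for subjects enrolled under global" (the sentence goes on to name the two amendments as separate groups).

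The two regimens differ in length. SAP 2.1 has treatment "twice daily (BID) for 12 or 16 weeks, according to the protocol version (amendment 1 or amendment 2, respectively"). SAP 6.3 places the "Follow-up Visit (Day 113 (Amendment 1) or Day 141 (Amendment 2")). Under both schedules (SAP Tables 1 and 2, footnote l), adverse events are collected to the last visit or to 30 days after the last dose, whichever is later. Observation therefore lengthens with treatment. Protocol 9.6.2 defines treatment-emergent events from the first dose and sets no closing day.

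SAP 7.7 then lists the measures:

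- **Main measure:** "Incidences and percentages will be provided on the subject-level (n"), overall and by system organ class and preferred term.
- **Rate:** "the number of AEs per patient-year of treatment will be calculated by nevanimibe dose".
- **Time ranges:** results are also split by time range, with the ranges chosen at the data review meeting for Cohort 1.
- **Kaplan-Meier curves:** optional, by dose and cohort; amendment is not named.

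SAP 7.9 reports mean exposure by amendment, but for the rate denominator says only: "The duration of treatment in subject-years will be calculated by cohort and by nevanimibe dose".

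**The concern.** The proportion of subjects with at least one event rises with the time they are watched. When one group is treated for a third longer and observed for a quarter longer, a difference in percentages mixes tolerability with duration. Amendment 2 also starts at 500 mg BID instead of 1000 mg BID (SAP 2.1), and Protocol 3.2 cites tolerability in support of that start. The split is where a reader would look for a tolerability gain, and the extra window pushes the percentage the other way. The mean time to onset (SAP 7.7; Table 14.3.1.7), if repeated by amendment, would also shift later under Amendment 2 simply because later onsets can be seen.

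**Working it through.** The documents give no adverse-event rate, power or exposure-adjusted figure for this comparison, so there is no stated figure to reproduce.

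**Inputs from the documents**

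| | Amendment 1 | Amendment 2 | Ratio |
|---|---|---|---|
| Weeks on drug (SAP 2.1) | 12 | 16 | 16/12 = 1.33 |
| Treatment plus 4-week follow-up (SAP Tables 1, 2) | 16 | 20 | 20/16 = 1.25 |
| Follow-up visit day (SAP 6.3) | 113 | 141 | 141/113 = 1.25 |
| End of treatment plus 30 days | 85 + 30 = 115 | 113 + 30 = 143 | 143/115 = 1.24 |
| Adverse-event contacts after Day 1 (SAP Tables 1, 2) | 7 | 9 | |

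**Assumptions:** one constant hazard, the same under both amendments; no dropout; Amendment 1 percentage p1 varied.

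**Formula:** p2 = 1 − (1 − p1)^k, with k = 1.25 if events arise over the whole observation window and k = 4/3 if they arise on treatment only. For example, 1 − 0.70^1.25 = 36.0%.

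| Amendment 1 | Amendment 2, k = 1.25 | Amendment 2, k = 4/3 |
|---|---|---|
| 10% | 12.3% | 13.1% |
| 30% | 36.0% | 37.8% |
| 50% | 58.0% | 60.3% |
| 80% | 86.6% | 88.3% |

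The largest gap is 8.2 points (p1 near 59%) over the observation window and 10.5 points (p1 near 58%) on treatment time only.

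**Break-even.** The percentages are equal when the Amendment 2 average hazard is 1/k of the Amendment 1 hazard: 16/20 = 0.80 or 12/16 = 0.75. A true reduction of 20-25% would show as no difference.

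**Time to onset.** With a hazard giving 30% by Day 113, mean onset among subjects with an event is about 53 days over a 113-day window and about 65 days over 141 days, with no real difference.

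**Whether the other measures fill the gap**

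- *Rate by dose.* Repeated within amendment, it still conditions on dose, and Amendment 2 changed the starting dose and titration. Amendment 1 schedules 1000 mg BID and then 1500 mg BID (SAP 2.2), so the 500 mg level has no scheduled Amendment 1 comparator. Rates within dose do not add up to an all-dose comparison.
- *Time ranges.* A common range could be picked, but SAP 5.4 puts the Cohort 1 meeting after that cohort's soft lock, in an open-label trial.
- *Mean exposure by amendment.* It shows the imbalance without adjusting for it.
- *Tables.* SAP Appendix 1 lists no adverse-event table by amendment and none labelled per patient-year. It also says the numbering and titles are not obligatory, so this is supporting evidence only.

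**A detail for the rate.** SAP 7.7 divides by treatment time. If follow-up events are counted in the numerator, an equal constant hazard gives an Amendment 2 to Amendment 1 ratio of (20/16)/(16/12) = 0.94, a small bias in the opposite direction. The two periods must match.

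**The case against.** Two stronger readings are tempting, and the documents support neither.

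A reader might infer that the SAP judges Amendment 2 on raw percentages alone. SAP 4.2 names no measure, and the analysis it repeats also includes the rate by dose and the time-range results. What stands is narrower: no all-dose adjusted comparison by amendment is specified.

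A reader might also infer that Amendment 2 must show more events. That needs an equal, roughly constant hazard. Amendment 2 starts at a lower dose, and Protocol 3.2 expects tolerability to improve with longer dosing. If Amendment 1 is at 50% and the Amendment 2 hazard is halved for the first four weeks and 20% lower thereafter, the exponent is (4 × 0.5 + 16 × 0.8)/16 = 0.925. Amendment 2 is then at 1 − 0.5^0.925 = 47.3%, which is fewer.

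Other objections carry weight:

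- The longer treatment is part of Amendment 2, so whole-regimen incidence is a legitimate quantity. That is a reason to keep it, but it cannot separate tolerability from duration.
- The summaries are exploratory (SAP 7), and no decision rule uses the split. With about 20-24 subjects and an assumed 10-12 per amendment, the standard error of the difference is about 15-22 points, larger than the bias. The bias nevertheless has a known direction and can be removed by specification.
- A first-84-days window is not neutral. Under SAP 2.2, 2000 mg BID is first available at Visit T3 (Day 57) in Amendment 1 and at Visit T4 (Day 85) in Amendment 2. The window keeps up to four weeks at that level for Amendment 1 and none for Amendment 2, so it should not be the main basis.

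**Conclusion.** The point holds as a gap in specification. The amendment comparison relies mainly on percentages over unequal periods, and the plan's other measures do not supply an all-dose, exposure-adjusted contrast. Under an equal constant hazard and no dropout, the longer window adds about 2 to 8 points for Amendment 1 rates of 10-80%, and at most 10.5 points if events occur only on treatment. These sizes are illustrative because the underlying rate is assumed. The actual difference could go either way. The consequence is limited by the exploratory status and small numbers, but the remedy is cheap enough to be worth making.

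**What to change.** Before final database lock, amend the SAP as follows.

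1. **SAP 7.9:** add subject-years by amendment.
2. **SAP 7.7:** report, by amendment across all doses, events per patient-year and subjects with a first event per patient-year at risk. State that numerator and denominator cover the same period, either treatment only or treatment plus follow-up.
3. **Whole-period percentages:** keep them as descriptive, with a footnote giving the unequal treatment and observation times.
4. **Supplement only:** events with onset in the first 84 days, with time to onset truncated there. Note that this window excludes Amendment 2's 2000 mg BID period while including Amendment 1's.

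The cost is SAP wording and small extra tables; the event and dosing dates are already collected. The downside is that per-time rates are most readily interpreted under a roughly constant hazard, and they will be imprecise with about 20-24 subjects.

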4.3 Stratification

While subjects will be enrolled into Cohort 1 or Cohort 2 based on the 17-OHP value at the initial screening visit as described above, no formal stratification of subjects will be performed and no prespecified enrollment targets have been set for either of the cohorts.

5. Data Handling

5.1 Handling of Missing Data and Outliers

Data will only be used as available (i.e., observed case data only will be used) and missing data will not be imputed unless specified otherwise.

During data recording and manual data checks, queries may be raised regarding implausible data. All queries will be closed prior to final database lock. The investigator will either confirm or correct the value. Subsequently, the corrected or confirmed value will be used for the analysis.

5.2 Handling of Withdrawals and Drop-outs

Subjects who terminate the study and are not considered evaluable (at least 8 weeks of continuous dosing and at least one post-baseline serum 17-OHP assessment) will be replaced. Data of subjects who prematurely terminated the study will be used as available.

5.3 Handling of Multiple Comparisons and Multiple Primary Variables

Not applicable.

5.4 Data Review

There will be a Data Review Meeting (DRM) using a database snapshot after the majority of sites have opened and there are sufficient data (e.g., at least 4-5 subjects with a minimum of 8 weeks on study drug). Additionally, there will be two DRMs, one after database soft lock for Cohort 1 and one after database soft lock for Cohort 2 and prior to hard lock of the database. All open queries and issues will be resolved prior to final database lock at the end of the study. All open questions/discrepancies for a subject that cannot be solved (even after consultation of the corresponding investigator (if applicable)), will be provided in a list to the sponsor for a case-by-case evaluation before final database lock. The definite classification of protocol deviations and the exclusion of subjects from the analysis set are reserved for the sponsor. It is important to note that, for the purpose of maintaining oversight over critical shortcomings, COVID-19-related protocol deviations are not marked as protocol deviations during the ongoing trial. They will, however, be recorded and a classification of COVID-19-related protocol deviations will be performed during the Data Review Meetings for Cohort 1 or Cohort 2.

6. Variables for Analysis

